7.2. Number of participants and study duration

Thirty to fifty patients will be recruited into the pilot RCT. The study will run for 16 weeks. During this 16-week, the patient in the intervention arm will:

- have access to the SAMSON mobile app (the first component of the intervention solution) throughout the study period, and
- receive initial pharmacist consultation and tele-consultations provided by their care team at Peter Mac, i.e nurses or pharmacists, in weeks 1, 4, 8 and 12.

All randomisations will be done by the study statistician.

Recruitment will be undertaken over a period of 6 months and the intervention is expected to be completed in ten months from recruitment commencement.

The patient in the controlled arm will receive usual care at the hospital (see details in section 7.9.2).

7.3. Study setting

The recruitment of, and data collection from, patients with cancer will take place at Peter Mac Parkville.

The questionnaire will be completed either in person or online.

7.4. Recruitment

7.4.1. Screening and recruitment

- Potentially eligible patients will be identified by site nurse/pharmacist, treating consultants, clinic lists and pharmacy dispensing records. Healthcare staff will be provided with an

Pilot Randomized Controlled Trial Study Protocol
Version 1.0 – 2 May 2023, Amendment 1 dated 26 June 2023

information flyer (Attachment 6) to introduce the study to patients who may be eligible and ask if they would like their details passed on for contact by the research team. If the patient is interested, the healthcare provider can refer their name and contact details to the study RC ([name]) for follow-up. The RC will meet the potential participant either in person outside the clinic or online to discuss the study.

- Through a comprehensive informed consent process, provided by the RC, patients will be informed that:
 - Participation in this research project is voluntary. Patients' decision about whether or not to take part, or to take part and then withdraw from this research project, will not affect their standard of care. Nor will it negatively affect their relationship with the treating team or any hospital services they receive now or in the future. If they withdraw, they will have the option to withdraw all their data from the study prior to publication.
 - Participants will be asked if they provide consent for their adherence data to be accessed by the treating clinician.
 - They will also be provided with Peter Mac's brochure "What happens to information about you?", because their medical record will be accessed as a part of this study.
 - Participants will receive a gift voucher of \$50 for their time spent to complete all surveys (control-arm participants: ASK-12, PAM-SF, PROMIS and FACT-G; intervention-arm participants: these four surveys and UTAUT). Participants may find the information and support that SAMSON provides to be useful. The findings of this research project will be used to improve the care of patients with cancers, or any other type of medical condition that requires the patient to take long-term medication.
- If the patient meets the inclusion criteria and agrees to participate, they will then sign the Participant Information and Consent Form (PICF) (see Attachment 1). Patients will also select the mode to complete surveys, i.e. either face-to-face, via mail or online. They will then be invited to complete the demographic survey (Attachment 2).
 - If the patient would like some time to consider taking part in the study, the RC will provide the patient with her email, should the patient wish to contact the RC to ask further questions, or if they wish to express their interest in taking part in the study. The RC will arrange to contact the patient in approximately 3-5 working days if no contact has been made by the patient during this time, to confirm whether or not the patient would like to take part in the study. After this time, if the patient contacts the RC to express interest in taking part, then consent procedures may be re-commenced as per the above. Otherwise, it will be interpreted that the patient has declined participation.
 - Reasons for declining participation will be recorded within a secure potential participant spreadsheet.

7.4.2. Participant withdrawal

The following are considered justified reasons for terminating participation of a participant in the study. Participants who meet any of these criteria will be defined as 'withdrawals'.

- Death
- Withdrawal of patient consent (Attachment 1)
- Stopping oral anti-cancer medicine under direction of the treating clinician. At point of consent, participants will be requested to inform the study team if this occurs. The RC will confirm this with the treating clinician before the patient is removed from the study.

Pilot Randomized Controlled Trial Study Protocol
Version 1.0 – 2 May 2023, Amendment 1 dated 26 June 2023

- The reason for study removal and the date the patient was removed will be documented in the participant spreadsheet.

7.5. Randomisation and allocation procedures

- Following consent, the study statistician (CI [name]), located at Swinburne University, will randomise participants 1:1 in blocks of 4 to intervention or usual care arms and send by email to the RC who will arrange participants to the arm specified in the email.
- All participants will be asked to provide their contact details for communication during the study and be provided with a unique identifying number and link to the online questionnaires to be completed within three days of consenting to participate in the trial. This set of questionnaires include: PAM-SF, PROMIS, FACT-G, and ASK-12 (Attachment 2). Participants can select the questionnaires in hard copy if they wish to.
- The RC will follow-up with participants to ensure questionnaires are completed. Following completion of the above questionnaires, the research assistant will advise the participant which study arm they were randomised to.
- If randomised to the intervention, participant patients will:
 - Be provided with the SAMSON mobile app user manual (Attachment 3a) to install the SAMSON mobile app onto their smartphone. They will also be given a password and username to access the SAMSON system. The RC will assist to download the APP and train them in how to use the SAMSON APP and webpage.
 - Receive an initial pharmacy consultation with the SAMSON trained pharmacist following the intervention manual (Attachment 4a). This consultation will be conducted either face-to-face, via phone or online.
 - Have their medication reminders and side effects surveys programmed into the app.
- Participants randomised to the control arm will be provided with pharmaceutical care as usual.

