Rational	
Optimal medication adherence (MA) is critical to treatment success and survival of patients with cancer. However, adherence rates to some anti-cancer regimens could be as low as 16% and often worsens overtime. Barriers to adherence are multi-faceted and require multi-dimensional interventions. Digital solutions can support complex interventions effectively and efficiently and are increasingly accepted by patients.
 
SAMSON is a novel patient-centred, comprehensive digital solution to improve MA in cancer. The solution consists of two synergistically operating elements:
 
 1. SAMSON mobile platform, including smartphone-based app to remotely prompt MA, monitor patient side-effects and deliver self-care advice; and computer-based app to enable adherence and side-effect reporting 2. Health professional tele-consultations, using motivational interviewing (MI) skills being trained via the motivational interviewing training platform (MITP) to promote patient's adherence and side-effect self-management. 
The SAMSON mobile app was tested on 30 people with haematological cancer at Peter Mac in 2021. The MITP was developed in 2022 and is being tested by healthcare professionals at Peter Mac.

Objectives	To evaluate the acceptability, feasibility (recruitment, randomisation, retention, intervention adherence and assessment processes) and potential efficacy of the SAMSON intervention solution among 30 to 50 patients with haematological, lung or melanoma cancer newly administered oral anti-cancer medicines.
Study design	
This is a pilot two-arm RCT. Recruitment will be undertaken over a period of six months and the intervention is expected to be completed in nine months from the recruitment commencement.
 
After completion of baseline questionnaires, participants will be randomised separately to either intervention or control groups (1:1 ratio), using a computer-generated randomisation chart. Participants in the intervention group will receive the SAMSON intervention solution, while those in the control group will receive usual care, for 12 weeks immediately following the randomisation.

Pilot Randomized Controlled Trial Study Protocol
Version 1.0 – 2 May 2023, Amendment 1 dated 26 June 2023

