7.1. Study design

This is a pilot two-arm RCT.

After completion of baseline questionnaires, participants will be remotely randomised to either intervention or control groups (1:1 ratio), using a computer-generated randomisation chart. Participants of the intervention group will receive the SAMSON intervention solution, while those in the control group will receive usual care, for 12 weeks immediately following the randomisation.

Primary outcomes:

- Intervention group: acceptability will be assessed at week 12.
- Both groups: Feasibility will be assessed throughout the study.

Secondary outcomes: adherence will be assessed at week 16. side-effect monitoring; toxicity self-management; anxiety, depression and symptoms; quality of life will be assessed at weeks 1 and 12; and optimal intervention strategy will be assessed at week 12.

Data collection and results reporting will be in line with the Consolidated Standards of Reporting Trials (CONSORT) criteria for pilot RCTs (Schulz et al., 2010).

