7.9.3. Procedure of data collection with questionnaires

The questionnaires as described in section 7.7 will be completed by all participants. Completion time for all of these questionnaires is approximately 30 minutes. All questionnaire reminders will be scheduled on REDCap to be sent out on days 4 and 8 after the initial notification is sent. The REDCap reminder will automatically stop once the survey is completed. If these questionnaires are still not completed in 10 days after initial participant notification, the RC will email the participant to remind them to complete or may contact the participant and ask if they would like to complete over

the phone. This will be the final attempt by the research team to encourage participants to complete the questionnaires. Any participants who don't complete the questionnaire after the final attempt will be treated as lost follow-up.

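### Section 7.5 randomises before the baseline questionnaires, section 7.1 and the synopsis after them; under 7.5 the recruiting coordinator can know the arm during baseline collection, and fixed printed blocks of 4 make about a third of allocations certain in advance

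*Protocol*

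**What the plan says.** The Protocol gives two orders of events.

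- Synopsis, study design: "After completion of baseline questionnaires, participants will be randomised separately to either intervention or control groups (1:1 ratio".
- Section 7.1: "After completion of baseline questionnaires, participants will be remotely randomised to either intervention or control groups (1:1 ratio".
- Section 7.5: "Following consent, the study statistician" acts, and "will randomise participants 1:1 in blocks of 4 to intervention or usual care arms and send by email to the RC". Participants then receive a "link to the online questionnaires to be completed within three days of consenting to participate in the trial"; the set is PAM-SF, PROMIS, FACT-G and ASK-12. Next, "The RC will follow-up with participants to ensure questionnaires are completed". Last, "Following completion of the above questionnaires, the research assistant will advise the participant which study arm they were randomised to".

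Section 7.9.3 schedules questionnaire reminders on days 4 and 8. If forms are still missing after 10 days, the RC makes a final contact and may offer completion by phone. Those who still do not "complete the questionnaire after the final attempt will be treated as lost follow-up".

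The RC's roles are spread over several sections. The RC meets and consents patients (7.4.1), checks eligibility (assessment schedule), receives each allocation and helps intervention patients install the app (7.5), and works with the principal investigator to submit the protocol (9.1). Recruitment is at one site (7.3). The statistician who allocates is at another institution (7.5).

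**The concern.** Whether allocation comes before or after the baseline measurement is an operational step, and the text gives two incompatible instructions for it. Randomisation is also one of the processes whose feasibility this pilot is meant to assess.

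If 7.5 is followed, two things can go wrong. The RC may hold the arm while pursuing baseline self-reports, so both the effort spent and the conduct of any phone completion could differ by arm. And a patient who never returns the forms is already in an arm, although no rule in 7.5 says how such a patient is handled.

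A second weakness does not depend on the timing. The person who takes consent sees every earlier allocation and has a document that prints the only block size. Late in a block, that person can know the next arm before deciding how to approach the next patient.

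At stake are the between-group comparisons of the secondary outcomes. Section 7.10 intends the results to inform the choice of endpoints and the sample size of the larger trial.

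**Working it through.** The plan states no figure on this point, so there is none to reproduce.

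**1. The two orders**

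| Step | Synopsis and 7.1 | 7.5 |
|---|---|---|
| 1 | Consent | Consent |
| 2 | Baseline questionnaires | Statistician randomises, arm emailed to RC |
| 3 | Randomisation | Questionnaires, followed up by RC |
| 4 | Assigned care starts | Participant told the arm |

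Step 4 of 7.5 speaks of the arm to which participants were already randomised, so the order in 7.5 is not merely loose wording.

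**2. Patients randomised but never told their arm, under 7.5**

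Number = N × (1 − completion). N = 30 and 50 come from the planned sample size. The documents give no expected baseline completion rate, so the rates below are assumptions; 70% and 50% are borrowed from the compliance thresholds in Table 1 to give a range.

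| Completion | N = 30 | N = 50 |
|---|---|---|
| 90% | 30 × 0.10 = 3 | 50 × 0.10 = 5 |
| 70% | 30 × 0.30 = 9 | 50 × 0.30 = 15 |
| 50% | 30 × 0.50 = 15 | 50 × 0.50 = 25 |

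**3. Predictability with fixed blocks of 4**

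Assume one list used in order of entry, and an observer who knows the block size and all earlier allocations. A 1:1 block has 6 equally likely arrangements: AABB, ABAB, ABBA and their mirror images.

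- Certain in advance: the 4th place always; the 3rd only when the first two match, in 2 of 6 arrangements. Share = (1 + 1/3)/4 = 1/3.
- Best guess correct, by place: 1/2, 2/3, 2/3, 1. Sum = 17/6; accuracy = 17/24 = 70.8%, against 50% by chance.
- N = 30 is seven full blocks plus two patients: 7 × 4/3 = 9.3 certain (31%). Guess accuracy = (7 × 17/6 + 1/2 + 2/3)/30 = 21.0/30 = 70.0%.
- N = 50 is twelve full blocks plus two: 12 × 4/3 = 16 certain (32%). Guess accuracy = (12 × 17/6 + 1/2 + 2/3)/50 = 35.17/50 = 70.3%.

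**4. What varying the blocks would change**

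For each N, 20,000 sequences were simulated, with a guesser who tracks only the running arm totals.

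| Blocks | N = 30 | N = 50 |
|---|---|---|
| Fixed 4 (size known, from step 3) | 70.0% | 70.3% |
| Random 4 or 6 | 68.8% | 69.0% |
| Random 2, 4 or 6 | 69.9% | 70.0% |

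Undisclosed varying sizes hide where a block ends and so remove most of the certainty, but average guessability hardly moves. Including size 2 gives up most of even that small gain.

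**The case against.** The strongest reply is that allocation is remote: a statistician at another institution randomises each patient only after that patient has consented, under either order. This stands. A reader might infer that concealment is broken, but nothing in the documents says the RC holds the list or sees a patient's arm before consent. What remains is prediction of later arms, which comes from the block size and the RC's dual role, not from the timing conflict.

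Other points for the plan also stand:

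- Site staff, clinic lists and dispensing records identify candidates (7.4.1), and the treatment team judges fitness and cognition (7.6.2). The RC's discretion begins at contact, eligibility checking and consent.
- Participants learn their arm only after completing the forms, and from the research assistant, so their own answers are given unaware of it. The exposure is on the RC's side.
- The main aims are acceptability and feasibility, and the outcome analysis is mainly descriptive (7.10).

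One might try to reconcile the sections by taking the baseline questionnaires in 7.1 to be the demographic form only, since the assessment schedule lists the four instruments at week 1. But 7.1 writes of questionnaires in the plural, and 7.5 wants these four within three days of consent and before the arm is disclosed, which makes them the pre-intervention measurement. Even on that reading, the RC would hold the arm while collecting them.

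**Conclusion.** The point holds in a limited form. The synopsis and 7.1 contradict 7.5 on when randomisation occurs. Under 7.5 the RC can know the arm during baseline collection, and patients can be lost between randomisation and disclosure. Separately, and under either order, about one third of allocations are certain in advance (about 9 of 30, 16 of 50), with a best guess right about 70 to 71% of the time. That figure rests on a single list in blocks of 4 and an RC who keeps track of earlier arms; it measures opportunity, not evidence that anyone would use it. The main exposure is in the between-group secondary comparisons.

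Three further inferences are tempting but not supported:

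- *That 30% of randomised patients would be lost.* The 70% in Table 1 is a feasibility threshold for each instrument, not an expected baseline completion rate. The losses are possible, and their number is unknown.
- *That the order in 7.5 lowers retention.* Section 7.7.1.2 divides by all who consent, so a patient who never completes baseline counts against retention under either order.
- *That 10/84 = 12% of the intervention period is used up waiting.* The 12-week clock starting at randomisation is stated in the synopsis and 7.1, where the forms are already complete. Section 7.5 plans three days (3/84 = 3.6%); ten days is the last-resort reminder.

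**What to change.** 1. Rewrite 7.5 to match 7.1 and the synopsis. The statistician releases an allocation only once the baseline questionnaires are recorded complete. Name PAM-SF, PROMIS, FACT-G and ASK-12 as that set, and align the assessment schedule.
2. Define the date of randomisation as day 0.
3. Report consented patients who never complete baseline as pre-randomisation losses. The retention denominator in 7.7.1.2 is all who consent; either keep it and say these patients count in it, or amend it explicitly.
4. As a secondary safeguard, use randomly varying block sizes, for example 4 and 6 but not 2, known only to the statistician, and remove the size from the protocol. This takes away most of the certainty about the next arm but lowers guessability only from about 70% to about 69%, so it should not be presented as a full cure.

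The cost is an edit to the wording and a regenerated list. The downsides are a slightly larger possible difference in arm sizes (up to 3 within an unfinished block of 6, against 2 in a block of 4) and a short wait for the allocation email.

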7.6. Study population

7.6.1. Inclusion criteria

All the following criteria must be satisfied for enrolment in the study.

- 1) A confirmed diagnosis of any-stage haematological, lung or melanoma cancer;
- 2) Scheduled to commence oral anti-cancer medicine(s) as part of routine care or commencing treatment/currently treated with the medication for less than 12 months;
- 3) Willing to have oral anti-cancer medicine(s) dispensed at Peter Mac;
- 4) Over 18 years old;
- 5) Proficient in English; and
- 6) Accessibility to the internet, a smartphone (and computer), and/or telehealth.

7.6.2. Exclusion criteria

Presence of any of the following criteria will exclude the participant from enrolment in the study.

- 1) Too unwell to participate in the study as determined by the patient's treatment team.

Pilot Randomized Controlled Trial Study Protocol
Version 1.0 – 2 May 2023, Amendment 1 dated 26 June 2023

- 2) Remaining treatment period of oral medications for cancer therapy is less than 12 months.
- 3) Demonstrated cognitive or psychological difficulties that would preclude study participation as defined by the treatment team's cognitive and/or psychiatric assessment or patient's disclosed medical history.

7.6.3. Concurrent participation

If the patient is already participating in another clinical trial (identified through the screening questionnaire or by their treating healthcare team), the PI of this trial and the PI of other trial will discuss whether one trial will impact adversely on the other.

7.7. Outcome assessments

7.7.1. Primary outcomes

7.7.1.1. Acceptability

We will assess clinicians' and patients' acceptability via a questionnaire, guided by the Unified Theory of Acceptance and Use of Technology (UTAUT) (Venkatesh et al., 2003; Venkatesh et al., 2012). The questionnaire will be adapted to assess determinants of clinicians' and patients' acceptance and use of the SAMSON, including: 1) *performance expectancy* (the degree to which clinicians believe that using the SAMSON will increase their ability to support patient adherence, while patients believe that using the solution will increase their knowledge, ability and confidence in medication treatment management); 2) *effort expectancy* (the degree of ease associated with using the SAMSON); 3) *social influence* (the extent to which clinicians and patients perceive that the SAMSON is considered socially acceptable); 4) *facilitating conditions* (the degree to which the organisational resources and support are available for clinicians and patients to use the SAMSON); and 5) *behavioural intention* (the degree to which clinicians and patients plan to use SAMSON in real life). Reliability metrics and validity analysis showed that UTAUT is a useful tool to assess the likelihood of success and to understand the drivers of acceptance of a new technology intervention (Venkatesh et al., 2003; Venkatesh et al., 2012). The theory is widely adopted and empirically validated in healthcare (Nguyen et al., 2016; Zhou et al., 2019). The questionnaire also includes some open questions for participants to provide more feedback and suggestions on the intervention solution. The questionnaire is adapted separately for healthcare professionals and patients.

7.7.1.2. Feasibility

The feasibility of the SAMSON intervention will be assessed by the research team at every stage of the trial, including recruitment, randomisation, retention, intervention adherence and assessment processes (Abbott, 2014; Leon et al., 2011). The RC will collect this data throughout the study. We will assess the feasibility quantitatively, using the traffic light approach (Table 1). Any outcome above the upper threshold will be deemed feasible. Any outcome below the lower threshold will be deemed as infeasible. Outcome(s) between the two thresholds will be considered for protocol changes to raise the measure above the upper threshold. This will inform overall feasibility for the future full RCT. Furthermore, the RC will also collect information from study nurses and pharmacists on issues and challenges that might raise during the study, and feedback that healthcare professionals and patients will provide in the UTAUT survey and use them to explain the quantitative results.

Table 1. Thresholds for traffic light approach to feasibility

Measures of feasibility	% Lower threshold	% Upper threshold
Recruitment rate	30	60

Pilot Randomized Controlled Trial Study Protocol
Version 1.0 – 2 May 2023, Amendment 1 dated 26 June 2023

Retention rate of study	70	80
Intervention adherence – patients:		
- Responding to medication reminders	70	90
- Responding to symptoms surveys	70	90
Data collection compliance:		
ASK-12	50	70
PAM-SF	50	70
PROMIS	50	70
FACT-G	50	70
UTAUT	50	70

Recruitment rate is defined as the number of patients recruited divided by the number of patients offered to join the study.

Retention rate of the study will be defined as the number of participants who remain at the end of the study divided by the total patients who consent to join the study.

